9.3.6. Menstruation Recovery

Status of menstruation recovery will be documented at the Follow-Up visit. Patients whose menses has not resumed as of the Follow-Up visit for whom there is no explanation for the lack of resumption (eg, medical procedure or medications) will be contacted again by telephone 3 (+0.5) months after the Follow-Up visit to determine if menses has resumed and will be asked about factors that may affect resumption of menses.

Menstruation recovery data will be presented in the table by pivotal phase 3 study treatment group for patients in the Extension Study Population. The table will include menstruation status during follow up, number of days to return of menses from last dose of study drug, and

explanation for the lack of menstruation resumption. Menstruation recovery data will also be provided in a by-patient listing,

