3.2. Safety Follow-Up Analyses

If the first menstruation after the end of study treatment administration is observed before the Follow-Up visit, the date of onset of the first menstruation is recorded in the eCRF. Patients whose menses has not resumed as of the Follow-Up visit for whom there is no explanation for the lack of resumption (eg, medical procedure or medications) will be contacted by telephone 3 months (+ 0.5 months) after the Follow-Up visit to determine if menses has resumed and will be asked about factors that may affect resumption of menses. If a patient is lost to follow-up, three documented attempts should be made to contact the patient by telephone. If unable to contact the patient by telephone, a certified letter must be sent to the patient.

Bone mineral density by DXA at 6-month and 12-month Post-Treatment will be proceed according to the rules mentioned in Section 2.1 Table 2. The follow-up bone densitometry will be submitted for central reading.

Post-treatment medical and gynecological history, concomitant medications, and bone fracture events will be measured at the 6-month and 12-month PTFU visits. Patients with PTFU scan bone loss $\geq 3\%$ at the lumbar spine and/or total hip compared with the pivotal study baseline will have the following clinical laboratory evaluations: vitamin D, thyroid-stimulating hormone, parathyroid hormone, creatinine, calcium, and phosphorous.

Data collected during the additional safety Follow-Up period that are available at the time of database lock for final analyses will be summarized and reported in the final clinical study report.

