4.2.1. Extension Study Population

The Extension Study population is defined as all patients who enrolled into MVT-601-3103 and who have received any amount of open-label study drug in MVT-601-3103. All efficacy analyses will be performed on the Extension Study population, unless otherwise specified. Efficacy analyses will be performed by treatment group as randomized in the pivotal phase 3 study.

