4.3.8. Visit Windows

Visit windows, which will be used to associate assessments with a scheduled visit, will be used only for summarizing data by visit. The windows for scheduled assessments are shown in [Table 3: Visit Windows for Monthly and Quarterly Assessments \(Monthly and Quarterly Visit, Lab and PGA\) \(Monthly and Quarterly Visit, Lab and PGA\)](#), [Table 4 \(BMD\)](#), [Table 5 \(electrocardiogram \[ECG\]\)](#), [Table 6 \(EHP-30\)](#), [Table 7 \(EHP work domain and EQ-5D-5L\)](#), [Table 8 \(PGIC\)](#), [Table 9 \(Endometriosis Biopsy\)](#), [Table 10 \(Mammogram\)](#), and [Table 11 \(eDairy\)](#) respectively. For safety assessments, the study day will be used to determine the associated visit window. There will be no separation of data from the pivotal phase 3 and extension study. For example, if an assessment in the extension study falls in the Week 24 visit window, it will be summarized as Week 24.

If the results from more than one assessment are within a given visit window, the non-missing result from the assessment closest to the target date will be used. If two assessments are equally close to the target day, the earlier assessment will be used. For summaries of shift from Baseline in safety parameters, all values will be considered for these analyses.

Table 3: Visit Windows for Monthly and Quarterly Assessments (Monthly and Quarterly Visit, Lab and PGA)

Visit	Start Day	Target Day	End Day
Week 4 ^a	1(2 ^b)	29	43
Week 8	44	57	71
Week 12	72	85	99
Week 16	100	113	127
Week 20	128	141	155
Week 24	156	169	183
Week 28	184	197	211
Week 32	212	225	239
Week 36	240	253	267
Week 40	268	281	295
Week 44	296	309	323
Week 48	324	337	351
Week 52	352	365	411
Week 65	412	456	502
Week 78	503	547	593
Week 91	594	638	684
Week 104	685	731	Date of last dose + 6 days
Safety Follow-Up ^c	Date of last dose + 7 days	Date of last dose + 30 days	Date of last dose + 60 days

^a Start day of Week 4 for study day 1 includes only post-Baseline assessments that occurred after the first dose.

^b For Patient Global Assessments (PGAs), the start day of the Week 4 visit window begins at Day 2.

^c The safety Follow-Up visit window will be restricted to assessments prior to the date of initiation of another investigational agent or hormonal therapy affecting the hypothalamic- pituitary- gonadal axis or surgical intervention for endometriosis-associated pain.

Table 4: Visit Windows for Bone Mineral Density Assessments

Visit	Start Day	Target Day	End Day

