9.3.8. Amenorrhea Rate and Sustained Amenorrhea Rate

Determination of amenorrhea will be based on a patient's daily menstruation status as reported in the eDiary. Amenorrhea for at least 56 consecutive days is defined as the lack of bleeding for at least 56 consecutive days after starting randomized study treatment in pivotal phase 3 study until Week 52. Amenorrhea for at least 28 consecutive days is defined as the lack of bleeding for at least 28 consecutive days after starting randomized study treatment in pivotal phase 3 study until Week 104. The study day when amenorrhea begins is defined as the first study day following the last reported day of menstruation. It will be assumed that there is no menstruation on days when menstrual status is not reported in the eDiary.

A summary of amenorrhea for at least 56 consecutive days will be provided by pivotal phase 3 study treatment group based on the following 56-day time intervals from pivotal phase 3 baseline through Day 365: Week 8 (Days 1 through 56), Week 12 (Days 29 through 84), Week 16 (Days 57 through 112), Week 20 (Days 85 through 140), Week 24 (Days 113 through 168), Week 28 (Day 141 through 196), Week 32 (Day 169 through 224), Week 36 (Day 197 through 252), Week 40 (Day 225 through 280), Week 44 (Day 253 through 308), Week 48 (Day 281 through 336), and Week 52 (Day 310 through 365). No analyses of 56-day amenorrhea after

Week 52 will be performed because some eDiary reporting cycles are less than 56 days. A summary of amenorrhea for at least 28 consecutive days intervals from pivotal study baseline through Day 731 will be provided by pivotal phase 3 study treatment group. The number and percentage of patients who are amenorrheic (ie, the amenorrhea rate) in each time interval will be presented. In each time interval, the numerator for the amenorrhea rate is the number of patients who did not bleed during the time interval; the denominator is the number of patients who remained on treatment during the entire time interval.

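### The menstruation recovery table pools women amenorrheic at end of treatment with women still menstruating, so it does not isolate recovery in suppressed women

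*SAP*

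**What the plan says.** Section 9.3.6 fixes the population of the table: "Menstruation recovery data will be presented in the table by pivotal phase 3 study treatment group for patients in the Extension Study Population". Section 4.2.1 defines that population as "all patients who enrolled into MVT-601-3103 and who have received any amount of open-label study drug", with no condition on menstrual status. The table is to show menstruation status in follow-up, "number of days to return of menses from last dose of study drug", and the explanation where menses did not resume.

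The recorded event is set in Section 3.2: "If the first menstruation after the end of study treatment administration is observed before the Follow-Up visit", its onset date goes into the eCRF. No preceding amenorrhea is asked for. A later telephone call is planned for "Patients whose menses has not resumed as of the Follow-Up visit for whom there is no explanation for the lack of resumption".

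Elsewhere the SAP does not take amenorrhea for granted. Section 7.2.6 has rules for women with menstruation days in the Week 52 and Week 104/EOT assessment periods. Section 9.3.7 classifies and counts bleeding on treatment. Section 9.3.8 treats amenorrhea as an outcome rate, with the definition beginning "Amenorrhea for at least 28 consecutive days is defined as the lack of bleeding for at least 28 consecutive days".

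**The concern.** Recovery and return are meaningful only for a woman whose periods had stopped. A woman still cycling at her last dose has nothing to recover, yet her next ordinary period fits the event in Section 3.2 and can enter the table as a return after a short interval. One case needs no assumed rate: a woman from the pivotal placebo group who takes a few open-label doses and stops belongs to this population, and her next period can count as recovery.

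This is the SAP's planned summary of how menses behave after up to 104 weeks of treatment. If women who were not suppressed are mixed in, the proportion returned and the days to return describe neither group. The table is laid out by pivotal treatment group, so unequal shares of still-menstruating women could also make the groups look different for reasons unrelated to recovery.

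A smaller gap sits beside this. Section 9.3.6 has no cut-off at the start of another hormonal therapy, investigational agent or relevant surgery, so bleeding that first occurs after such a start can be taken as return of menses.

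**Working it through.** **The plan's own figures.** The SAP states no figure for recovery or amenorrhea. Its only size figure is enrolment in Section 2.2: 0.67 × 1200 = 804, consistent with the stated 800 or so. It does not enter the argument.

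**Text check.**

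1. Population: any open-label dose (4.2.1, applied in 9.3.6).
2. Event: first menstruation after end of treatment (3.2).
3. Restriction or stratum by menstrual status at last dose: none in 3.2, 4.2 or 9.3.6.
4. Comparable summaries restricted to women at risk: yes. Dyspareunia NRS change is limited to women with a non-zero baseline score (7.3.2), and exposure-adjusted event rates use women at risk of a first occurrence (9.1.8).
5. Cuts at new therapy or surgery: applied to biopsies (Table 9 footnote a) and to adverse event collection (9.1), but absent from 9.3.6.

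**Direction and completeness.** Let s be the share suppressed at last dose, and P_s and P_n the proportions with recorded return in suppressed and still-menstruating women. The table shows

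P = s × P_s + (1 − s) × P_n.

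P exceeds P_s whenever P_n exceeds P_s. If they are equal (say 95% and 95%), the proportion is not biased at all. All inputs below are assumptions.

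| s | P_s = 80%, P_n = 98%: table shows | Non-return shown (20% in suppressed) | P_s = 90%, P_n = 98%: table shows |
|---|---|---|---|
| 0.9 | 0.9 × 80 + 0.1 × 98 = 81.8% | 18.2% | 90.8% |
| 0.8 | 83.6% | 16.4% | 91.6% |
| 0.7 | 85.4% | 14.6% | 92.4% |
| 0.6 | 87.2% | 12.8% | 93.2% |
| 0.5 | 89.0% | 11.0% | 94.0% |

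With 10% missing follow-up kept in both denominators (P_s = 80%), the all-women table gives 0.9 × 83.6 = 75.2% at s = 0.8 and 0.9 × 87.2 = 78.5% at s = 0.6, against 0.9 × 80 = 72.0% in suppressed women. The absolute level falls; the contrast stays.

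**Time to return.** Assume log-normal times in suppressed women (log SD 0.35) and next menses uniform over days 1 to 28 in still-menstruating women. The 28 days borrow the typical cycle mentioned in 7.2.6. The pooled median m solves

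s × Φ(ln(m / median) / 0.35) + (1 − s) × min(1, (m − 1) / 27) = 0.5.

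| Median in suppressed women | Pooled, s = 0.9 | Pooled, s = 0.5 |
|---|---|---|
| 28 days | 26.8 | 21.7 |
| 32 days | 30.5 | 23.2 |
| 40 days | 38.1 | 25.4 |

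Check of one cell: for 32 days and s = 0.9, Φ = (0.5 − 0.1) / 0.9 = 0.444, so m = 32 × exp(−0.140 × 0.35) = 30.5.

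**The case against.** The strongest reply is that the step from recorded to counted is not in the text. Section 3.2 says only that a date is recorded, and Section 9.3.6 names a status summary without listing its categories. The eCRF is not shown and may separate women who never stopped from women who resumed. This stands, which is why the point is that such women can be counted as returned, not that they will be.

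Several stronger readings are tempting and should not be drawn:

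- **That the SAP expects many women to bleed on drug.** It provides for such women but forecasts no share. Tabulating an outcome is not a prediction of its frequency.
- **That non-return is understated by exactly the share still menstruating.** That holds only if every such woman has a recorded return. If 5% of them have none, a true 10% shows as 0.9 × 10 + 0.1 × 5 = 9.5% with one tenth still menstruating, and 0.6 × 10 + 0.4 × 5 = 8.0% with four tenths, rather than 9% and 6%.
- **That explanations are sought only from women who never resumed.** Women telephoned at three months are also asked about factors affecting resumption, which covers those who resumed between the visit and the call.
- **That Table 3 footnote c already forbids counting bleeding after new therapy.** It says "The safety Follow-Up visit window will be restricted to assessments prior to the date of initiation of another investigational agent or hormonal therapy" and continues with surgery, but Section 4.3.8 uses these windows only for by-visit summaries. It does not govern an event date. Table 9 footnote a and Section 9.1 are better precedents, though they too concern other data.

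It is also true that recovery of menses is not among the Table 1 endpoints, that everything here is descriptive, that the count of women not resumed does not change with the denominator, and that a by-patient listing is planned. These limit the importance. They do not make the pooled summary describe recovery.

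**Conclusion.** The point holds in a limited form. As written, the table mixes women whose menses were suppressed with women who had nothing to recover. Relative to suppressed women, under the same denominator rules, it would tend to show faster and more complete return. That direction rests on still-menstruating women bleeding sooner, and having a recorded return more often, after stopping. The first is plausible because their next period falls within about one cycle; the second is an assumption.

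The size cannot be obtained from the SAP. The tables above only show what different assumed shares would do. Regular 28-day cycles in women bleeding on hormonal treatment are themselves an assumption that the SAP does not support. Nor can a reader infer that the absolute percentage returned must be too high: missing follow-up and explained non-resumption may stay in the denominator and pull it down.

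This is a cheap improvement to a supportive descriptive safety table. No primary endpoint, error rate or power is affected.

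**What to change.** In Section 9.3.6, keep the all-patient column and add the same summaries, within pivotal treatment group, for:

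- (a) women amenorrheic at end of treatment, named as the column that describes recovery;
- (b) women still menstruating at end of treatment;
- (c) women whose status cannot be determined.

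Define (a) as no bleeding in the last 28 eDiary-collected days on drug, using days with an entry actually reported. The Section 9.3.8 convention that an unreported day is a day without menstruation should not be carried over, because it would label poor reporters as amenorrheic. After Week 52 the diary runs only in four cycles, so where last dose falls outside a cycle use the menstruation CRF completed at each visit (Section 7.2.3), and state which visit applies.

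Add that bleeding first occurring after the start of another hormonal therapy, investigational agent or relevant surgery is flagged and not counted as return of menses, in line with the cuts in Table 9 footnote a and Section 9.1.

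The cost is SAP wording and extra columns, using data already collected. The columns are smaller, and the recovery figures are likely to be slightly less favourable.

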9.3.7. Analysis of Bleeding Profiles

Bleeding profile categories will be determined based on the amount of bleeding experienced by patients as reported in the eDiary. When a patient is menstruating, the amount of bleeding during the past 24 hours is captured daily in the eDiary with five response options: spotting, light, moderate, heavy, and extremely heavy. It will be assumed that there is no bleeding on days that the patient either uses the eDiary and reports that she is not menstruating, or when the patient misses reporting menstruating within eDiary cycle. The responses to the eDiary question about the amount of bleeding will be used to define the bleeding profile categories (Table 25).

After Week 52, to reduce patient burden, eDiary data were collected over four eDiary collection cycles on the following schedule: Week 57 to the Week 65 visit, Week 71 to the Week 78 visit, Week 85 to the Week 91 visit, and Week 98 to the Week 104 visit. After the Week 104 visit, patients continued daily eDiary entry until the 30-day Follow-Up visit.

Table 25: Definitions of Bleeding Profile Categories

Bleeding Profile Category	Category Definition
Irregular bleeding	3 to 5 bleeding/spotting episodes and less than 3 bleeding-free intervals of least 14 days during a bleeding-profile period
Prolonged bleeding	Bleeding/spotting episodes of more than 14 days during a bleeding-profile period
Frequent bleeding	More than 5 bleeding/spotting episodes during a bleeding-profile period
Infrequent bleeding	1 or 2 bleeding/spotting episodes during a bleeding-profile period
No bleeding	No bleeding during a bleeding-profile period
Normal bleeding	None of the above definitions are met

^a Bleeding/spotting episode: at least one day with bleeding or spotting reported, bounded by bleeding-free intervals.

^b Bleeding-free interval: at least two consecutive days with no bleeding or spotting reported, bounded by bleeding/spotting episodes.

The number and percentage of patients belonging to each of the bleeding profile categories defined in Table 25 will be summarized by pivotal phase 3 study treatment group over four bleeding-profile periods: Days 1 through 90, Day 91-Day 180, Day 181-Day 270, and Day 271-365. A patient must have at least 90 days of treatment exposure to be included in the summary of each period. No analyses of bleeding profile after Day 365 will be performed because all of the eDiary reporting cycles are less than 90 consecutive days.

Summaries of bleeding intensity and number of bleeding days based on 28-day intervals will be provided from the last 28 days starting from the pivotal phase 3 baseline through Day Day 731. The following 28-day windows will be used for summaries of bleeding during the randomized treatment period: Week 4 (Days 1 through 28), Week 8 (Days 29 through 56), Week 12 (Days 57 through 84), Week 16 (Days 85 through 112), Week 20 (Days 113 through 140), Week 24 (Days 141 through 168), Week 28 (Days 169 through 196), Week 32 (Days 197 through 224), Week 36 (Days 225 through 252), Week 40 (Days 253 through 280), Week 44 (Days 281 through 308), Week 48 (Days 309 through 336), Week 52 (Days 338 through 365), Week 65

(Days 429 through 456), Week 78 (Days 520 through 547), Week 91 (Days 611 through 638) and Week 104 (Days 704 through 731). Only patients who were on study drug for all days in a given 28-day window will be included in the summary for that window. The specific summaries of bleeding that will be provided are described in Table 26.

Table 26: Summaries of Bleeding Amount and Number of Bleeding Days

Bleeding outcome	Type of summary
Bleeding amount (or intensity), defined numerically as: Spotting = 1 Light = 2 Moderate = 3 Heavy = 4 Extremely Heavy = 5	Mean, SD, median, minimum, maximum; based on all eligible patients who report bleeding in the eDiary.
Number of bleeding days	Mean, SD, median, minimum, maximum; based on all eligible patients, regardless of whether any bleeding is reported in the eDiary.
Number of bleeding days by the following bleeding amount (or intensity) categories: No bleeding Spotting Light Moderate Heavy Extremely Heavy	Mean number of days per category.

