7.2.6. Derivation of Responder Status at Week 52, Week 104/EOT and Missing Data Handling Rules

For the primary efficacy analysis, both primary endpoints will incorporate the missing data handling rules at Week 52, Week 104/EOT as follows (Table 14, Table 15 and Figure 2):

- For patients missing eDiary for all visits in the extension study, their Baseline/Week 24 responder status from the pivotal phase 3 study will be carried over as their responder status to Week 52, Week 104/EOT.
- For patients who have any pain score entries in eDiary in the extension study, responder status for DYS and NMPP will be derived as follows:
 - For DYS, the responder status will be defined using the following rules taking analgesic use into consideration (Table 14):
 - If there are at least 2 days of DYS NRS scores reported in the eDiary, then the average will be calculated and used in the assessment of the DYS responder status. Requiring a minimum of 2 days of DYS NRS scores is considered reasonable since a typical menstrual cycle has bleeding days ranging from 3 to 7 days.
 - If there are < 2 days of NRS scores for DYS reported in the eDiary, then the following scenarios will be considered:
 - If no DYS scores are reported in the eDiary, then the data collected on the menstruation eCRF will be considered as follows:
 - If no menstruation is reported on the eCRF, then the average DYS score will be set as 0;
 - Otherwise, if any menstruation days are reported on the eCRF, then the average DYS score will be set as missing and will be imputed using a mixed-effects model.

- If only one DYS score is reported in the eDiary, then the data collected on the menstruation eCRF will be considered as follows:
 - If no more than one menstruation day is reported on the eCRF, then the observed DYS score will be taken as the average DYS score;
 - If more than one menstruation day is reported on the eCRF, then the average DYS score will be considered missing and will be imputed using a mixed-effects model.
- For NMPP, the responder status will be defined using the following rules, taking analgesic use into consideration (Table 15):
 - If there are at least 14 days of scores for NMPP reported in the eDiary, then the average NMPP score will be used in the assessment of the NMPP responder status. Requiring minimum 14 days of NMPP scores is considered reasonable since this corresponds to at least half of the non-menstrual days from a typical 28-day menstrual cycle.

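### SAP Table 25 as footnoted: a bleeding-profile period with exactly three episodes is always Irregular, so a regular 28-day cycle is called Irregular or Normal according to where the period starts

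*SAP*

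**What the plan says.** SAP Section 9.3.7 assigns each patient and period a bleeding-profile category from Table 25, by pivotal-study treatment group. The periods are "Days 1 through 90, Day 91-Day 180, Day 181-Day 270, and Day 271-365", that is, three of 90 days and one of 95.

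The categories that matter here are:

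- Irregular: "3 to 5 bleeding/spotting episodes and less than 3 bleeding-free intervals of least 14 days during a bleeding-profile period".
- Infrequent: "1 or 2 bleeding/spotting episodes during a bleeding-profile period".
- Normal, the residual: "None of the above definitions are met".

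Footnote a defines an episode as "at least one day with bleeding or spotting reported, bounded by bleeding-free intervals". Footnote b defines a bleeding-free interval as "at least two consecutive days with no bleeding or spotting reported, bounded by bleeding/spotting episodes". Neither footnote says what happens when the start or end of a period cuts an interval or an episode.

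Elsewhere (Section 7.2.6, missing-data rules for the primary endpoints) the SAP gives its own picture of ordinary menses: "a typical menstrual cycle has bleeding days ranging from 3 to 7 days", and a 28-day cycle described as typical ("at least half of the non-menstrual days from a typical 28-day menstrual cycle").

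**The concern.** The second half of the Irregular rule is meant to separate 3 to 5 well-spaced episodes from 3 to 5 badly spaced ones. If an interval counts only when an episode inside the period lies on each side, that test is empty at three episodes: there are never three intervals to find. One or two episodes are Infrequent, so Normal then needs at least four episodes in about 90 days. A woman with a regular monthly cycle often shows only three.

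At stake is the split between Normal and Irregular in a safety table read by treatment group and by period. Irregular would be inflated and Normal deflated wherever regular menses persist. That is chiefly the former placebo group in Days 1-90 and 91-180, which largely cover the 24-week randomized period. It would distort the pattern against which bleeding on relugolix + E2/NETA is read.

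**Working it through.** The SAP states no figure to reproduce, so the check applies Table 25 to perfectly regular bleeding.

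**Inputs.** Period length L = 90 or 95 days (Section 9.3.7). Cycle length c = 28 days and bleeding days b from 3 to 7 (Section 7.2.6). Cycle lengths of 24, 26, 30 and 32 days are assumptions, used only to show the range.

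**Step 1: the counting argument.** With n episodes in a period, at most n − 1 intervals lie between them. For n = 3 this is 2, and 2 < 3, so the period is Irregular whatever the interval lengths. For n = 4 there are 3 intervals. In a 28-day cycle each lasts 28 − b = 21 to 25 days, so all reach 14 days and the period is Normal.

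**Step 2: how often three rather than four.** Let the first menses in the period start on day s, with s ≤ 1 if it began on or before Day 1. At least one of its days falls in the period if s ≥ 2 − b. The fourth menses starts on day s + 3c, which must be ≤ L. The number of starting phases with four menses is therefore L − 3c + b − 1. For c = 28, all remaining phases have three.

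| L | b | Four menses: Normal | Three menses: Irregular | Share Irregular |
|---|---|---|---|---|
| 90 | 3 | 90 − 84 + 2 = 8 | 20 of 28 | 71% |
| 90 | 5 | 90 − 84 + 4 = 10 | 18 of 28 | 64% |
| 90 | 7 | 90 − 84 + 6 = 12 | 16 of 28 | 57% |
| 95 | 3 | 95 − 84 + 2 = 13 | 15 of 28 | 54% |
| 95 | 5 | 95 − 84 + 4 = 15 | 13 of 28 | 46% |
| 95 | 7 | 95 − 84 + 6 = 17 | 11 of 28 | 39% |

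Direct enumeration of every starting phase gives the same counts. For the same woman with 5-day menses, the share drops from 64% to 46% only because the fourth period is five days longer.

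**Step 3: does footnote a change this?** If menses cut by the period edge are not counted as episodes but still bound an interval, the 28-day shares are unchanged.

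**Step 4: assumed cycle lengths.** With 5-day menses and L = 90, the Irregular share is 38% at 26 days, 87% at 30 and 94% at 32. The size depends strongly on cycle length.

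**Step 5: two ways to count edge intervals.**

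- *Truncated length only:* an interval cut by the period edge counts if the part inside lasts at least 14 days. At 28 days the Irregular share is 0% for 3, 5 or 7 bleeding days, at L = 90 and at L = 95. For L = 90 it is 0%, 7% and 13% at 30 days, and 12.5%, 19% and 25% at 32 days.
- *Full length:* an edge interval counts, measured with the eDiary days outside the period. The share is 0% at 24, 26, 28, 30 and 32 days, for 3, 5 or 7 bleeding days and both period lengths.

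**The case against.** The strongest objection is that the narrow reading is not compelled. Footnote b does not say that both bounding episodes must fall inside the period. eDiary entry is daily to Week 52, so for most period edges the programmer can see the neighbouring episode. If edge intervals are bounded that way and counted when only partly inside the period, the problem vanishes for regular 24- to 32-day cycles. Footnote a even points towards this: three episodes each bounded on both sides imply four intervals, not two, so within a single period the two footnotes define each other in a circle at the edges. This stands in part. A reader might infer that the SAP's text forces the mislabelling, and it does not quite. But the SAP states no rule for looking outside the period, and its wording about intervals during a bleeding-profile period favours the narrow reading. Two careful programmers could report 0% or 64% from the same diary.

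Two stronger inferences are tempting and are not supported. The first is that all ordinary monthly bleeding becomes Irregular: at 28 days, 29% to 43% of phases in a 90-day period show four menses and are Normal. The second is that the split between Normal and Irregular carries no information: with four or five episodes the 14-day condition still discriminates.

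It is also fair that the consequence is limited. No formal comparisons are planned (Sections 4.1 and 7.1), the table feeds no primary or secondary efficacy endpoint, and bleeding days, bleeding amount and amenorrhea are summarised without Table 25.

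**Conclusion.** The point holds for Table 25 read within the period. A period with exactly three episodes is then Irregular by construction. For the SAP's typical 28-day cycle with 3 to 7 bleeding days, this mislabels 57% to 71% of starting phases in a 90-day period and 39% to 54% in the 95-day one. The label then follows the position of the period's first day rather than the regularity of bleeding.

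The shares assume perfectly regular cycles and equally likely phases. They describe regular bleeders only and do not predict the percentages in the table, since amenorrheic women on treatment are unaffected. The effect is confined to one descriptive safety summary, mainly the former placebo group up to Day 180. It is worth correcting because the rule gives a wrong label and the repair is small.

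**What to change.** In Table 25, footnotes a and b, state that a bleeding-free interval touching the start or end of the bleeding-profile period counts. Its length should be measured with the adjacent eDiary days outside the period where these exist. Where they do not, it counts if the part inside the period is at least 14 days. State also that an episode cut by the period edge counts as an episode, which removes the circularity.

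The fallback will be needed after Day 365, because Section 7.2.4 requires no diary entry again until Week 57. Used alone it is adequate at 28 days but leaves up to 25% Irregular at an assumed 32 days in a 90-day period, so it should not be the main rule.

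As a secondary consistency point, a fourth period of Days 271-360 would make all four equal, at the price of leaving five days out of this table.

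The cost is one amended footnote pair and a derivation change. Section 1 says the methods are consistent with the pivotal studies. If their bleeding tables used the same footnotes, which cannot be seen here, the report should note the difference so that the two sets are not compared directly.
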